5.2.2. Analyses for Continuous Data

The co-primary efficacy endpoints will be analyzed using an ANCOVA model, with model terms for Baseline score, Baseline diary average pain, index joint (knee or hip), highest Kellgren-Lawrence grade, and treatment group, and study site as a random effect. The assessment of significance for the tanezumab SC versus placebo treatment contrasts will use a step-down testing strategy within each of the co-primary efficacy endpoints defined as first testing tanezumab 2.5/5 mg versus placebo, and if statistically significant ($p \leq 0.05$) to then test tanezumab 2.5 mg versus placebo. Finally, a tanezumab treatment group is declared as superior to placebo if the corresponding treatment contrast is significant over all three co-primary endpoints. This testing procedure will maintain the Type I error to 5% or less within each of the co-primary efficacy endpoints, and to less than 5% for all three co-primary efficacy endpoints. An additional (main effects ANCOVA) analysis for each of the co-primary efficacy endpoints will use a per-protocol analysis set, which will exclude subjects who are major protocol deviators.

The primary analysis of the co-primary endpoints will use multiple imputation for missing data, to account for uncertainty around the subject response. The basis for imputing missing values will be dependent on the reasons for missing data. For subjects with missing data due to discontinuation prior to Week 16 for lack of efficacy or for an adverse event or death, imputation will be based on sampling from a normal distribution using a mean value equal to the subject's Baseline efficacy value and the standard deviation (over all treatment groups) of the observed efficacy data at Week 16. For subjects with missing data for any other reason, imputation will be based on sampling from a normal distribution using a mean value of the subject's last observed efficacy value and standard deviation (over all treatment groups) of the observed efficacy data at Week 16. Imputed values for the Patient's Global Assessment of Osteoarthritis will be rounded to integer values from 1 to 5. Imputed values for WOMAC Pain and Physical Function will be truncated at 0 and 10. One hundred imputation samples will be used, and the ANCOVA model described above will be used for each imputation dataset. The final results will be calculated using the combined sets of results from each imputation dataset analysis.

The primary analysis set is the Intent to Treat analysis set. These three primary endpoint analyses will be used to assess the primary objective of the study.

The mixed model ANCOVA, with multiple imputation, will also be used with other continuous change from Baseline endpoints for landmark (single time point) analyses. The model will include the covariates described in [Section 3.4.1](#), including study site as a random effect. Estimates of treatment effects and pair-wise treatment comparisons will be based on least squares means (LS means) and 95% confidence intervals (CI) will be provided.

A number of sensitivity analyses will be performed on the primary efficacy endpoints in order to assess the robustness of the conclusions for the primary objective. These relate to the analyses for missing data and the analysis population, the homogeneity of the results across factors that may influence efficacy, and for a secondary analysis of the PGA. The analyses described below will not be subject to the testing strategy described for multiple comparisons of the primary analyses. As such, assessment of all treatment comparisons will be made independent of results over the three co-primary endpoints or the two treatment comparisons for each analysis.

Primary Endpoint Sensitivity Analyses

The ITT analysis set is used in the analyses numbered 2 and 3 below, and Per-Protocol analysis set used in analysis number 1 below.

(1) Per-Protocol Analysis Set

The primary analysis using multiple imputation described above will be repeated, but using the Per-Protocol analysis set in place of the ITT analysis set. This analysis will assess the robustness of the efficacy conclusions to subjects who have more strictly adhered to protocol inclusion and exclusion criteria, and to protocol defined study procedures.

(2) Alternative Missing Data Analyses

There are four additional analyses that will assess the robustness of the efficacy conclusions to the choice of multiple imputation as the primary method for accounting for missing data.

In the first and second analyses, the primary ANCOVA analysis model described above will be repeated, but using BOCF and LOCF respectively for missing data (note these are single imputation analyses).

The third sensitivity analysis for the primary endpoints will use a mixed model repeated measures analysis using the observed and imputed data up to Week 16 from the primary multiple imputation analysis, with covariate terms for Time (study week, treated as a categorical variable), Treatment Group and Time-by-Treatment interaction, as well as the covariates described in [Section 3.4.1](#). The unstructured covariance will be used in the modeling of the within-subject errors in the analysis. Even though this is a sensitivity analysis for the primary endpoints, estimates for the time points of Weeks 2, 4, 8, and 12, in addition to Week 16 will be shown from this analysis. See Appendix 2.1 for details on windows.

The fourth sensitivity analysis for the primary endpoints will use a mixed model repeated measures analysis using all observed data up to Week 16 (i.e. retrieved dropout), with covariate terms for Time (study week, treated as a categorical variable), Treatment Group and Time-by-Treatment interaction, as well as the covariates described in [Section 3.4.1](#). The unstructured covariance will be used in the modeling of the within-subject errors in the analysis.

A summary of the missing data pattern will be shown for the WOMAC Pain and Physical Function subscales and the PGA over Baseline and Weeks 2, 4, 8, 12, and 16. This summary will show the incidence of subjects with each pattern of observed and missing data over these visits and endpoints. This summary will be shown overall, and split by treatment group.

(3) Interaction Analyses

Interaction analyses will be performed for the co-primary endpoints, exploring the effect of Study site and Country. These analyses will fit the covariate terms described in [Section 3.4.1](#) (except for use of Study site as a covariate in the Country interaction analysis, where Country will be used instead [as a fixed term]), in addition to the interaction term of treatment group by factor.

The interaction of Treatment with Study site will be fitted as a random effect (in addition to Study site itself), with the resulting estimated treatment differences being shown for the largest (pertaining to enrollment) study sites to illustrate the level of consistency of treatment benefit across the larger study sites. The study sites to be examined in this way will be any site with an average of four or more subjects per treatment group within the site, which for this study relates to any site with 12 or more subjects in total. This assessment will be made prior to unblinding, therefore a study site in this group may still have fewer than four subjects

in one or more of the treatment groups, however that site will still be included in this summary of efficacy of the largest study sites. To aid the interpretation of the treatment-site and treatment-country interactions, a summary of the efficacy data for each co-primary endpoint by treatment group will be shown for the sites with ≥ 12 subjects and for the countries in this study (USA, Canada, and Puerto Rico [summarized separately from other USA sites]).

Other time points for the primary efficacy measure

The ANCOVA model described above for the co-primary endpoints, using covariates of Baseline score, Baseline diary average pain, Index Joint, Highest KL grade (2, 3 or 4) and Treatment, with Study Site as a random variable, will be used in the analysis of WOMAC Pain, WOMAC Physical Function and PGA for the change from Baseline to Weeks 2, 4, 8, and 12. This analysis will be produced using multiple imputation, and BOCF and LOCF for missing data.

The MMRM analyses described above will also analyze results for the secondary time points of Weeks 2, 4, 8, and 12, for the co-primary efficacy endpoints.

Secondary Endpoint Analyses

Other secondary endpoints include the WOMAC Stiffness subscale, WOMAC Average score and WOMAC Pain subscale items (Pain When Walking on a Flat Surface, and Pain When Going Up or Down Stairs), all conducted for the change from Baseline to Weeks 2, 4, 8, 12 and 16. Analysis of Average Pain in the index joint will be conducted for the change from Baseline to Days 1, 2, 3, 4, 5, 6, and 7, and to Weeks 1, 2, 3, 4, 6, 8, 10, 12 and 16. The analysis of these endpoints will use the same ANCOVA analysis as described above for the co-primary endpoints, with multiple imputation for missing data, and using the additional covariate of baseline diary average pain score.

The rescue medication data will be converted to Weekly scores for the week prior to the timepoint of interest. Calculation of the endpoints is described in Appendix 3.

The ... number of days of use of rescue medication ... will be analyzed for Weeks 2, 4, 8, 12, and 16... and the amount of rescue medication use per week will be analyzed for Weeks 2, 4, 8, 12, and 16. ... The number of days and amount of rescue medication (mg dosage of acetaminophen) will be analyzed using the Negative Binomial model, with model terms of Baseline WOMAC Pain subscale score, Baseline diary average pain score, index joint, Kellgren-Lawrence grade, and treatment group. In this model the error term is defined with a negative binomial distribution, and 'log' is used as the link function. Estimated levels of rescue medication use will be shown for each treatment group, and the ratio (with 95% CI) for comparisons versus placebo will be shown. Imputation for missing rescue medication data will use LOCF only. For this analysis, Baseline data will not be carried forward in the case of a post-Baseline observation not being available for use in LOCF.

A table showing number and percentage of subjects will summarize the response for each dimension (item) for the EQ-5D-5L™ at Baseline and Week 8 and Week 16. These summary tables will be shown by treatment group. In addition, for each treatment and for each time point assessed, descriptive statistics (mean, standard deviations, median, number of subjects) will characterize the five-item health status profile on the EQ-5D-5L™ in terms of the health utility score, and the EQ-Visual Analog Scale (EQ-VAS).

The HCRU data at Baseline, Week 24, and Week 40 will be summarized.

Summaries of the change from Baseline to Week 16 in the WPAI:OA impairment scores will be shown by treatment group. This summary will use observed data only (no imputation for missing data). The calculation of these endpoints is described in Appendix 3.

The summary will show number and % of subjects with a decrease, no change, and an increase in score for the change from Baseline to Week 16 as well as descriptive statistics (mean, standard deviation, median, number of subjects) of the Baseline and change at Week 16. The 4 WPAI parameters will be analyzed using the ANCOVA model described above for the primary endpoint using covariates of the corresponding Baseline score, Baseline diary average pain, Index Joint, Highest KL grade (2, 3 or 4), and Treatment, with Study Site as a random variable.

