2.2. Study Design

The study design is summarized in the diagram below.

Figure 1. Study Design

This is a randomized, double-blind, placebo-controlled, multicenter, parallel-group, Phase 3 study of the efficacy and safety of tanezumab when administered by SC injection for 16 weeks compared to placebo in subjects with osteoarthritis of the knee or hip. Approximately 690 subjects (approximately 230 per treatment group) will be randomized to one of 3 treatment groups in a 1:1:1 ratio. Subjects will receive a total of two SC injections, separated by 8 weeks:

- *tanezumab 2.5 mg (Day 1) and tanezumab 2.5 mg (Week 8);*
- *tanezumab 2.5 mg (Day 1), and tanezumab 5 mg (Week 8);*
- *placebo to match tanezumab (Day 1) and placebo to match tanezumab (Week 8).*

The randomization will be stratified by the factors of index joint and highest Kellgren-Lawrence grade in the knee and hip joints.

This study is designed with a total (post-randomization) duration of 40 weeks and will consist of three periods: Screening (up to a maximum of 37 days), Double-blind Treatment (16 weeks, 6 in-clinic visits), and Safety Follow-up (24 weeks). The Screening Period (to begin up to 37 days prior to Randomization) includes a Washout Period (lasting a minimum of 2 days for all prohibited pain medications) if required, and an Initial Pain Assessment Period (IPAP; 7 days prior to Randomization/Baseline; minimum 3 days).

The end of treatment period is at Week 16, with the safety follow-up period up to Week 40. The primary time point for efficacy is Week 16. The period of interest for most safety results is the treatment period. Selected safety results will also be provided separately for the safety follow-up period, and some results will be provided for the combined overall study period comprising the treatment and safety follow-up periods.

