3.4.1. Covariates

For all models analyzing the continuous primary and secondary efficacy endpoints (except rescue medication) the corresponding Baseline value will be used as a covariate, in addition to Baseline diary average pain. Study site will be fitted as a random effect in the ANCOVA models. The randomization stratification variables of index joint (hip or knee) and highest Kellgren-Lawrence grade (2, 3 or 4) will be included as fixed effects.

A listing of subjects with mis-matches between the stratification variables entered at randomization and the case report form data (including central lab data for Kellgren-Lawrence grade) will be provided. In analysis models, the strata entered at randomization will be used, but for descriptive summarization of the population and identification of subgroups, the strata as indicated on the case report form data will be used.

For the models analyzing the amount and number of days of rescue medication use the model will include terms for Baseline WOMAC Pain, Baseline diary average pain and stratification factors.

The analysis of the incidence of treatment discontinuation due to lack of efficacy will include ... model terms for Baseline WOMAC Pain subscale score, Baseline diary average pain score, index joint, Kellgren-Lawrence grade, and treatment group.

For categorical/binary response endpoints relating to WOMAC Pain and PGA, the corresponding Baseline WOMAC Pain or PGA value will be used as a covariate in the analysis model, in addition to the stratification parameters of index joint and highest Kellgren-Lawrence grade, as well as Baseline diary average pain. For the OMERACT response endpoint, the Baseline WOMAC Pain subscale score and Baseline diary average pain score will be used as covariates in the analysis model, in addition to the stratification parameters of index joint and highest Kellgren-Lawrence grade.

Additional analyses of the three co-primary endpoints will examine the treatment interactions with Study site and Country.

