Change from Baseline to Week 16 in Patient Global Assessment of Osteoarthritis	ITT	ANCOVA	BL Score, BL diary average pain, Index Joint (Knee/Hip), Highest KL grade (2, 3 or 4), Treatment Group (Study site as a random effect)	LOCF	Sensitivity Analysis
Change from Baseline to Weeks 2, 4, 8, 12, and 16 in WOMAC Pain subscale	ITT	MMRM	BL Score, BL diary average pain, Index Joint (Knee/Hip), Highest KL grade (2, 3 or 4), Time, Treatment Group, Time x Treatment Group (Study site as a random effect)	Multiple Imputation Data	Sensitivity Analysis for Week 16 (Secondary Endpoint Analysis for other time points)
Change from Baseline to Weeks 2, 4, 8, 12, and 16 in WOMAC Physical Function subscale	ITT	MMRM	BL Score, BL diary average pain, Index Joint (Knee/Hip), Highest KL grade (2, 3 or 4), Time, Treatment Group, Time x Treatment Group (Study site as a random effect)	Multiple Imputation Data	Sensitivity Analysis for Week 16 (Secondary Endpoint Analysis for other time points)
Change from Baseline to Weeks 2, 4, 8, 12, and 16 in Patient Global Assessment of Osteoarthritis	ITT	MMRM	BL Score, BL diary average pain, Index Joint (Knee/Hip), Highest KL grade (2, 3 or 4), Time, Treatment Group, Time x Treatment Group (Study site as a random effect)	Multiple Imputation Data	Sensitivity Analysis for Week 16 (Secondary Endpoint Analysis for other time points)
Change from Baseline to Weeks 2, 4, 8, 12, and 16 in WOMAC Pain subscale	ITT	MMRM	BL Score, BL diary average pain, Index Joint (Knee/Hip), Highest KL grade (2, 3 or 4), Time, Treatment Group, Time x Treatment Group (Study site as a random effect)	All Observed Data Including Off-Treatment	Sensitivity Analysis for Week 16 (Secondary Endpoint Analysis for other time points)
Change from Baseline to Weeks 2, 4, 8, 12, and 16 in WOMAC Pain subscale	ITT	MMRM	BL Score, BL diary average pain,	All Observed	Sensitivity Analysis for

12, and 16 in WOMAC Physical Function subscale			Index Joint (Knee/Hip), Highest KL grade (2, 3 or 4), Time, Treatment Group, Time x Treatment Group (Study site as a random effect)	Data Including Off-Treatment	Week 16 (Secondary Endpoint Analysis for other time points)

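### Both MMRM sensitivity analyses force one baseline slope on all visits; adding Baseline-by-Time terms would match the Week 16 adjustment to the primary ANCOVA at almost no cost

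*SAP*

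**What the plan says.** Section 5.2.2, item (2), describes two repeated-measures models. The third sensitivity analysis works on complete data, "using the observed and imputed data up to Week 16 from the primary multiple imputation analysis". The fourth uses everything observed to Week 16, on or off treatment, and leaves missing values missing. Both have "covariate terms for Time (study week, treated as a categorical variable), Treatment Group and Time-by-Treatment interaction, as well as the covariates" of Section 3.4.1. That section says "the corresponding Baseline value will be used as a covariate, in addition to Baseline diary average pain", with no by-time term. For the covariance, "The unstructured covariance will be used in the modeling of the within-subject errors in the analysis".

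Appendix 1 agrees. Its six MMRM rows (three co-primary endpoints, two data sets) give "BL Score, BL diary average pain, Index Joint (Knee/Hip), Highest KL grade (2, 3 or 4), Time, Treatment Group, Time x Treatment Group", with site as a random effect. Time by Treatment Group is the only interaction.

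The ANCOVAs in the same section are fitted one time point at a time: Week 16 for the primary, BOCF and LOCF analyses, and Weeks 2, 4, 8 and 12 separately. Each therefore estimates its own baseline slope.

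**The concern.** Section 5.2.2 presents these MMRMs as a check on how far the conclusions depend on the primary missing-data method. As written they also change the baseline adjustment, from a slope specific to Week 16 to one averaged over five visits. If MMRM and ANCOVA disagree at Week 16, part of the gap could come from that restriction.

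In the fourth analysis there is a further issue. A likelihood-based MMRM copes with dropout that depends on observed data only if its mean model is right. A wrong common slope is a mean-model error, and uneven dropout can turn it into bias. This is the only one of the four alternatives that uses neither carried-forward values nor the primary imputations, so it should be free of an avoidable restriction. Both models also supply estimates at Weeks 2 to 12.

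**Working it through.** **Inputs from the SAP.** Model terms and unstructured covariance as above; five post-baseline visits; 2-sided 5% tests; "Approximately 690 subjects (approximately 230 per treatment group) will be randomized to one of 3 treatment groups in a 1:1:1 ratio". The SAP gives no figure for the cost of this choice, so there is none to reproduce.

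**Assumed inputs.** Baseline SD 1.2 or 2.0; residual SD 2.2; true Week 16 effect -0.6 (negative favours tanezumab). Baseline slope from first to last visit: flat, moderate decline (0.75 to 0.45), strong decline (0.95 to 0.35), or moderate rise. Week 16 missingness is none, or 11 to 33% by arm.

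**Step 1: complete data (stands in for the third analysis).** Let b16 be the true Week 16 slope and b the fitted common slope. The model omits (b16 - b) x (Baseline - mean). Randomisation balances Baseline, so the contrast is not biased, but the residual variance rises by (b16 - b)² x Var(Baseline).

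- With visit-specific slopes: SE = sqrt(2 x 2.2² / 230) = 0.205.
- Moderate decline, b = 0.599: sqrt(1 + 0.149² x 1.44 / 4.84) = 1.003. Simulated SEs: 0.2055 against 0.2048.
- Strong decline, b = 0.643: sqrt(1 + 0.293² x 1.44 / 4.84) = 1.013. Simulated: 0.2074 against 0.2049, ratio 1.012.
- At baseline SD 2.0 the simulated ratios are 1.009 (moderate) and 1.034 (strong). With flat slopes the ratio is 1.000.

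For power under strong decline at SD 1.2: 0.6/0.2049 = 2.93, so power is Φ(2.93 - 1.96) = 83.4%; 0.6/0.2074 = 2.89 gives 82.5%. The loss is about one point.

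**Step 2: incomplete data (fourth analysis).** Maximum-likelihood MMRMs with unstructured covariance were fitted with a common slope and with visit-specific slopes. The table gives the shift in the Week 16 contrast (common minus visit-specific) from runs with 60,000 per arm at baseline SD 1.2.

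| Dropout pattern | Moderate decline | Strong decline | Moderate rise |
|---|---|---|---|
| None | +0.001 | -0.001 | -0.001 |
| Completely random | +0.001 | -0.002 | -0.002 |
| Same score-dependent rule in all arms | -0.004 | -0.011 | +0.005 |
| Score-driven on placebo, random on tanezumab | -0.029 | -0.061 | +0.027 |
| Score-driven on tanezumab, random on placebo | +0.020 | +0.048 | -0.021 |
| More high-baseline placebo subjects lost | -0.054 | -0.100 | +0.054 |
| More high-baseline tanezumab subjects lost | +0.042 | +0.077 | -0.041 |
| More low-baseline placebo subjects lost | +0.052 | +0.099 | -0.052 |

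With flat slopes the shift is at most 0.002 in size. A shift of 0.10 is 0.10/0.6 = 17% of the assumed effect. At 230 per arm and SD 2.0, strong decline with score-driven placebo dropout gives -0.16. With dropout the SE rises by about 0 to 2.6% at SD 1.2, and by 5.4% in the strong-decline case at SD 2.0.

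**Limits.** One baseline covariate was used; site, index joint and Kellgren-Lawrence grade were left out. The scale is WOMAC-like, so there is no figure for the 1-to-5 PGA.

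**The case against.** The specification is explicit and consistent between Sections 3.4.1 and 5.2.2 and Appendix 1, so this is a modelling refinement and not a contradiction. Visit-specific adjustment is already planned in the ANCOVAs at every visit, so the Weeks 2 to 12 results do not rest on the MMRMs alone. Section 5.2.2 places these analyses outside the multiplicity strategy. The fourth model also keeps off-treatment data, and Section 5.2 plans a Week 16 collection even for a subject who stops after the Day 1 dose, so missingness may be lower than assumed here. All of this stands, and it limits the severity. It does not give a reason to prefer the restricted model.

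A reader might go further and infer that the restriction tilts the all-observed-data result toward tanezumab. The SAP does not support that. Such a tilt needs two conditions together, such as a slope that declines over visits and dropout that takes more high-score or high-baseline subjects from placebo than from tanezumab. That is plausible, but the SAP states neither condition, and the table shows other patterns giving no shift or the opposite sign.

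Nor does the SAP say that the link to Baseline weakens over time. In the third analysis its own rule may work against this: values missing after death, adverse event or lack of efficacy are drawn around the subject's own Baseline, which strengthens the later relation as such cases accumulate.

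**Conclusion.** The point holds as a low-severity improvement. It is certain from the text that both MMRMs impose one slope per baseline covariate on Weeks 2 to 16 and so adjust differently from the landmark ANCOVAs. The consequences are conditional. If the slope changes over visits, the Week 16 SE is higher by about 0 to 1.2% with complete data at baseline SD 1.2, and by about 5% at the extreme examined. If dropout in the all-observed-data model also depends on score or baseline and differs by arm, the contrast can move by about -0.10 to +0.10 points at that SD, in either direction. The restriction causes no bias in the imputed-data MMRM. These sizes rest on assumed SDs, slopes, effect and dropout. The primary analysis and the key secondary endpoint are untouched.

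**What to change.** Add two terms, Baseline score by Time and Baseline diary average pain by Time, to the third and fourth sensitivity analyses in Section 5.2.2, item (2), and to the six MMRM rows of Appendix 1. Report the treatment contrast at each visit with both covariates held at their overall means.

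Each covariate then has five slopes in place of one, so the cost is 2 x (5 - 1) = 8 degrees of freedom with about 690 subjects, plus a short text edit. If the slopes prove constant, almost nothing is lost: the simulated SEs were then the same to within about 0.1%.
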